1.2.3.2 Subjects with Hereditary Angioedema

One clinical study with CSL312 is ongoing in subjects with HAE.

CSL312_2001 is an ongoing multicenter, randomized, placebo-controlled, parallel-arm, phase 2, dose ranging (75 mg, 200 mg, and 600 mg) study to investigate the efficacy, PK, and safety of CSL312 SC administered every 4 weeks as prophylaxis to prevent HAE attacks in subjects with C1-INH HAE or FXII/Plasminogen HAE. The study consists of a Screening Period, a Run-in Period, 2 Treatment Periods (Treatment Period 1 [TP1] [2 parts: 1 double-blind part and 1 open-label part] and open-label Treatment Period 2 [TP2]), and a Follow-up Period. After the Run-in Period, eligible subjects with C1-INH HAE were randomized to 1 of 4 treatment groups (placebo, or 75 mg, 200 mg, or 600 mg CSL312) in double-blind TP1. Subjects received a single IV loading dose of investigational product followed 1 week later by a single SC injection of investigational product once every 4 weeks for 12 weeks (for a total of 13 weeks). In open-label TP2, subjects receive a single SC injection of either 200 mg or 600 mg CSL312 every 4 weeks (for a total of 44 weeks). Currently the study is ongoing and the randomized, double-blinded part of TP1 has been completed.

A total of 32 patients with C1-INH HAE type 1 or type 2 were enrolled in the randomized double-blind treatment arms of TP1 at 20 study sites across 5 countries. Interim results from TP1 demonstrate that CSL312 is safe and well tolerated at all 3 doses and has an overall favorable safety profile. All 3 dose levels of CSL312 SC every 4 weeks achieved clinically meaningful reduction in the HAE attack rate compared to placebo. The most frequent AEs were non-serious ISRs (ie, injection site erythema, pruritus, swelling, and discomfort) that were mild or moderate in severity. No SAEs or AEs of special interest (AESIs, severe hypersensitivity and anaphylaxis, TEEs, bleeding events) were reported.

No difference in the PK of CSL312 was noted between healthy subjects in Study CSL312_1001 and subjects with HAE in Study CSL312_2001.

All eligible subjects who successfully complete Study CSL312_2001 may have the opportunity to enroll in an open-label phase 3b study of CSL312 in subjects with HAE (CSL312_3002).

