10.1 Sample Size Estimation

In total, 60 subjects are planned to be randomized.

Forty subjects with C1-INH HAE type 1 and type 2 completing the 6-month Treatment Period are needed to achieve a power of approximately 90% for a two-sided Wilcoxon Test (alpha of 5%). Subjects will be randomized to the Active Arm or the Placebo Arm with a ratio of 3:2. An attack rate per month of 0.3125 for CSL312-treated subjects and of 1.3 for subjects receiving placebo are assumed. The monthly attack rates of placebo and of CSL312 are assumed to be Poisson distributed.

It is targeted to randomize approximately 5 adolescents into the treatment period with a randomization ratio of 3:2 (active:placebo).

To allow for sufficient safety data, to increase the likelihood of adolescents entering the study and, to have at least 40 subjects reaching the end of the study, an additional 20 subjects are planned to be randomized.

In case it is not feasible to randomize the targeted number of adolescents, the targeted total sample size will be achieved by randomizing the needed number of adult subjects.

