4.5 Determination of the Sample Size

In total, 60 subjects are planned to be randomized.

Forty subjects with C1-INH HAE type 1 and type 2 completing the 6-month Treatment Period are needed to achieve a power of approximately 90% for a two-sided Wilcoxon Test (alpha of 5%). Subjects will be randomized to the Active Arm or the Placebo Arm with a ratio of 3:2. An attack rate per month of 0.3125 for CSL312-treated subjects and of 1.3 for subjects receiving placebo are assumed. The monthly attack rates of placebo and of CSL312 are assumed to be Poisson distributed.

The sample size calculation is performed with SAS 9.4 using proc power procedure with twosamplewilcoxon test=WMW which performs power analyses for the Wilcoxon-Test for two independent groups, i.e. the CSL312 and the Placebo treatment in Study CSL312_3001. The Wilcoxon Rank Sum test is testing from departure from the null hypothesis and is assessing if there is a location shift between the distributions of the HAE attack rates of the CSL312 and the Placebo treatment. SAS Proc Power procedure uses the O'Brien-Castelloe approach to compute approximate power. Alpha is set to 5% [O'Brien & Castelloe, 2006]. The assumed monthly attack rates of placebo and of CSL312 (i.e. 1.3 and 0.3125 attacks/month, respectively) are used as the two means of the two Poisson distributions. The randomization ratio of 3:2 was implemented by GROUPNS = (24 16) resulting in a total sample size of 40 which is the lowest one reaching 90% power.

It is targeted to randomize approximately 5 adolescents into the treatment period with a randomization ratio of 3:2 (active:placebo).

To allow for sufficient safety data, to increase the likelihood of adolescents entering the study and, to have at least 40 subjects reaching the end of the study, an additional 20 subjects are planned to be randomized.

In case it is not feasible to randomize the targeted number of adolescents, the targeted total sample size will be achieved by randomizing the needed number with adult subjects.

In addition, it is targeted to include 5 Japanese subjects into the total 60 subjects randomized.

Based on Method 1 and Method 2 in the [Basic principles on Global Clinical Trials] the sample size of the Japanese subjects are planned as below. The point estimate of the endpoint in each arm for Japanese population and other regions (for Method 2) are assumed as the same as that for the global population.

Method 1

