With setting the notations of treatment differences between CSL312 and placebo arm as D, the treatment difference in the global population as D_{all} , and the treatment difference in the Japanese subpopulation as D_{Japan} , the probabilities of $D_{Japan}/ D_{all} > 0.5$ were calculated for the settings that the global sample size is 60 patients (CSL312 arm = 36 patients, and placebo arm = 24 patients) including the Japanese sample size of 5 – 8. The Japanese sample sizes of each arm were rounded based on the 3:2 randomization ratio.

Table 4 Sample Size Justification for Japanese Subjects - Method 1

Japanese sample size			Probability (%) of $D_{Japan}/ D_{all} > 0.5$	
Total	CSL312	Placebo	With median	With mean
5	3	2	64	70
6	4	2	63	71
7	4	3	65	76
8	5	3	73	76

Method 2

With setting the notations of treatment differences between CSL312 and placebo arm as D, the treatment difference in the global population as D_{all} , the treatment difference in the Japanese subpopulation as D_{Japan} and the treatment difference in other regions x as $D_{other-x}$, the probabilities of that all of the global, Japan and other regions of $D > 0$ were calculated for the settings that the global sample size is 60 patients (CSL312 arm = 36 patients, and placebo arm = 24 patients), the Japanese sample size is 5 – 8, the sample size of North America and Europe are assumed to be the same. The sample sizes of each arm for Japan and other regions were rounded up based on 3:2 randomization ratio.

Table 5 Sample Size Justification for Japanese Subjects - Method 2

Sample size for each region			Probability (%) of all of D >0	
Japan	North America*	Europe*	With median	With mean
5	27	28	75	86
6	27	27	73	85
7	26	27	70	91
8	26	26	67	92

* Expected that the sample sizes for North America and Europe would be the same. If not divisible, the sample size of Europe includes one more patients than that of North America.

As the results, if the Japanese sample size is 8, the probabilities to achieve consistency between the Japanese subset and the global population are 67%–92% using mean and median with 3:2 randomization ratio based on Method 1 and 2. Eighty percent probability would be achieved with 5 Japanese patients already when using the mean and Method 2.

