10.1 Analysis of Primary Endpoint

The primary endpoint is the time-normalized number of HAE attacks per month during the Treatment Period from Day 1 (first study drug administration) through Day 182 (inclusive).

Subjects will enter HAE symptoms into their eDiary, the start and end date and time, the interference of HAE symptom(s) with daily activities, and location(s) of the HAE symptom(s). Investigator-reported HAE attacks will be based upon review of subject diaries, relevant interval medical history, and physician judgment. The investigator may ask clarifying questions to assist in his/her assessment of whether or not an HAE attack occurred. If an attack occurred, then the investigator will record an attack in the eCRF form, the start/end date and time, the attack location(s), and the severity of the attack based on the most severe symptoms. For every visit, the investigator will report all HAE attacks that have occurred in the interim since the last visit the subject attended.

For all analyses considering HAE attacks, only the HAE attacks confirmed and reported by the investigator using the eCRF ‘HAE Attacks’ form will be used.

HAE attacks with a start date on or after the first day of the Run-in Period but prior to the date and time of the first study drug administration will be counted for the Run-in Period.

HAE attacks with a start date and time after the first study drug administration through Visit Day 182 (inclusive) or End of Study visit (whatever is first) will be counted for the Treatment Period and will be included in the analyses of efficacy.

The primary endpoint will be analyzed using the ITT and PP Analysis Set. The ITT Analysis Set will be used as the primary analysis and the PP Analysis Set will be used as the supplementary analysis (see [Section 10.1.3](#)).

The primary endpoint, time-normalized number of HAE attacks per month, is calculated per subject as:

$$[\text{the number of HAE attacks} / \text{length of subject treatment in days}] * 30.4375$$

where the length of subject treatment is calculated as:

$$[\text{the date of Study Visit Day 182 or the End of Study date [whatever is first]} - \text{the date of Study Visit Day 1 of the Treatment Period} + 1].$$

To transform the length of subject treatment which are calculated in days in years the number of days is divided by 365.25. Thus, time-normalized number of HAE attacks per year is calculated per subject as:

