$$[\text{the number of HAE attacks} / \text{length of subject treatment in days}] * 365.25.$$

The time-normalized number of HAE attacks will not be calculated if the subject's observation time for the Treatment Period is less than 30 days, i.e. subject discontinued within 30 days after first study drug administration.

The randomization is stratified by the variables age (≤ 17 years, > 17 years) and, for adults, the subject's baseline attack rate (1 to < 3 attacks/month, and ≥ 3 attacks/month) during the Run-in period. Age and baseline attack rate are not regarded as confounder or effect modifier. The stratification by age is implemented to mitigate the risk that adolescent subjects could be randomized all to the same treatment, with worst case scenario that all adolescents are on placebo treatment. There is no significant physiological basis to suggest different efficacy or safety profiles in adults and adolescents and the distribution of attack locations in adolescent subjects typically mirrors that of adults [[MacGinnitie, 2014](#)].

It is expected that around 50% of subjects will have 1 to < 3 attacks/month and around 50% of subjects will have ≥ 3 attacks/month as baseline attack rate [[Banerji, 2018](#)]. Because of the stratified randomization these two subgroups of subjects will be equally distributed to the Active and to the Placebo arm. It is assumed that the treatment effect, i.e. the time-normalized number of HAE attacks observed under CSL312 treatment, is not impacted by the baseline attack rate. Nevertheless, the time-normalized number of HAE attacks will be compared for

the 6 months of the Active Arm and the 6 months of Placebo Arm using a Poisson Regression model including baseline attack rate as fixed effect in a sensitivity analysis, see [Section 10.1.2](#).

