10.1.2 Primary Efficacy Analysis

Following the estimand described in [Section 10.1.1](#), the primary efficacy endpoint between CSL312 and placebo is tested for a difference by comparing the time-normalized number of HAE attacks in the 6 months of the Active Arm and in the 6-month Placebo Arm period by using a two-sided Wilcoxon Test (Hierarchical Testing H01). The monthly CSL312 dose will be evaluated against monthly placebo at alpha = 5%:

$$H_{01}: a_1 = 0 \text{ versus } H_{11}: a_1 \neq 0$$

In the above hypothesis, the term “ a_1 ” is the shift between the 2 distributions of monthly CSL312 and monthly placebo.

The time-normalized number of HAE attacks per month and per year will be summarized descriptively for the 6 months of the Active Arm and the 6-month Placebo Arm period by median and mean with corresponding 95% CIs.

Sensitivity Analysis considering baseline attack rate

As a sensitivity analysis, the time-normalized number of HAE attacks will be compared for the 6 months of the Active Arm and the 6 months of the Placebo Arm using a generalized linear model (GLM) for count data assuming a Poisson distribution with the logarithm as link function and Pearson chi-square scaling of standard errors to account for potential over dispersion. The model includes treatment (categorical) and the time-normalized baseline attack rate during Run-in Period (continuous) as covariates. To account for the length of subject treatment, the logarithm of the length of subject treatment is used as an offset variable in the model:

$$\log \lambda_i = \log(t_i) + \beta' x_i$$

where λ_i is the expected number of HAE attacks of subject i ($i = 1, \dots, n$ with n the number of subjects in ITT Analysis Set), $\log(t_i)$ is the offset with t_i as the length of the i -th subject treatment in days and x_i is the covariate of subject i which includes the time-normalized baseline attack rate of subject i and the treatment information of subject i .

From this model, the least squares mean time-normalized number of HAE attacks and the standard errors are estimated for CSL312 and placebo. The mean time-normalized number of HAE attacks ratio for CSL312 relative to the placebo and the corresponding 95% confidence interval are also estimated. To report as mean attack rate per month, the received estimates are transformed by the exponential function and scaled by time.

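### The 90% power for 40 completers is calculated on one-month Poisson counts, not on the Day 1–182 primary endpoint, and no between-subject dispersion is stated

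*SAP*

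**What the plan says.** Protocol 10.1 states: "Forty subjects with C1-INH HAE type 1 and type 2 completing the 6-month Treatment Period are needed to achieve a power of approximately 90" per cent, for a two-sided Wilcoxon test at 5% with 3:2 allocation. It assumes Poisson attack rates of 0.3125 per month on CSL312 and 1.3 per month on placebo.

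SAP 4.5 repeats this and gives the implementation: SAS PROC POWER, Wilcoxon–Mann–Whitney, O'Brien–Castelloe method. On the inputs, which are Poisson means, it says: "The assumed monthly attack rates of placebo and of CSL312 (i.e. 1.3 and 0.3125 attacks/month, respectively) are used as the two means". On the result: "GROUPNS = (24 16) resulting in a total sample size of 40 which is the lowest one reaching 90% power". A further 20 subjects bring the total to 60, for safety data, adolescent recruitment and having 40 reach the end of the study.

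SAP 10.1 defines the primary endpoint as the number of attacks from Day 1 through Day 182, divided by days observed and multiplied by 30.4375.

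Tables 4 and 5 in SAP 4.5 give consistency probabilities for 5 to 8 Japanese subjects without naming an observation period. The text concludes: "Eighty percent probability would be achieved with 5 Japanese patients already when using the mean and Method 2".

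**The concern.** A subject's one-month Poisson count and a six-month Poisson count rescaled to a month have the same mean, but the second has about one sixth of the variance. The distribution entered in the power calculation is therefore not that of the endpoint. Neither the 90% nor the statement that 40 is the smallest adequate total applies to the trial's primary test.

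The calculation also assumes that subjects within an arm share one rate. SAP 10.1 expects baseline rates to split about evenly at 3 attacks per month, and the sensitivity model in SAP 10.1.2 uses "Pearson chi-square scaling of standard errors to account for potential over dispersion". The SAP assumes that the CSL312 rate does not depend on the baseline rate, but that still leaves heterogeneity in the placebo arm. Over six months, between-subject variation rather than Poisson noise largely determines power, and the plan gives no value for it.

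At stake is the stated justification for the 40 completers and for the Japanese subset. No hypothesis test depends on Tables 4 and 5, because the Japanese efficacy analyses in SAP 10.2 are descriptive.

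**Working it through.** **Inputs.** Rates 0.3125 and 1.3 per month, Poisson, 24/16, two-sided 5% (SAP 4.5). Exposure 182 / 30.4375 = 5.98 months (SAP 10.1). All dispersion values below are assumptions; the documents give none.

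**Step 1: reproduce the plan's figure (one month).** Poisson means 0.3125 and 1.3.

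| Split | O'Brien–Castelloe | Simulated Wilcoxon, tie-corrected |
|---|---|---|
| 21/14 | 0.872 | 0.87–0.88 |
| 24/16 | 0.907 | 0.92 |

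Among exact 3:2 totals, 40 is the first to reach 90%. Without that restriction, 23/16 (39 subjects) already gives 0.903.

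**Step 2: same rates over 182 days.**
- Means: 0.3125 × 5.98 = 1.87 and 1.3 × 5.98 = 7.77.
- Variance of the monthly rate on placebo: 1.3 for one month; 1.3 / 5.98 = 0.22 for six.
- Subjects with no attacks, exp(−mean): 73% (CSL312) and 27% (placebo) for one month; 15% and 0.04% over 182 days.
- Power at 24/16: 0.9995 by O'Brien–Castelloe, about 1.00 by simulation.
- Power at 6/4: 0.897 by O'Brien–Castelloe, 0.92–0.94 by simulation with and without continuity correction. At 9/6: 0.958 and above 0.99.
- The smallest 3:2 total reaching 90% is thus 10 to 15, depending on the method. Normal approximations are rough at that size.

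**Step 3: add between-subject variation (182 days).** Negative binomial, variance = mean + k × mean². Simulated power:

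| k | Both arms, 24/16 | Both arms, 36/24 | Placebo only, 24/16 | Placebo only, 36/24 |
|---|---|---|---|---|
| 0.5 | 0.99 | >0.99 | 0.99 | >0.99 |
| 1 | 0.88 | 0.97 | 0.82 | 0.94 |
| 2 | 0.59 | 0.77 | 0.35 | 0.46 |

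With k in both arms, 24/16 gives 90% at k of about 0.95. Neither document presents the one-month window as an allowance of that kind.

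**Step 4: Tables 4 and 5.** Simulated with 100,000 trials per row, 36/24 overall.
- One month, Table 4, Japanese n = 5, 6, 7, 8. Median: 63.9, 63.2, 65.4, 73.2 (stated 64, 63, 65, 73). Mean: 70.8, 70.4, 75.6, 76.0 (stated 70, 71, 76, 76).
- One month, Table 5, mean: 86.0, 84.4, 91.9, 92.1 (stated 86, 85, 91, 92).
- One month, Table 5, median: about 74, 75.2, 70.9 and 67 to 70 (stated 75, 73, 70, 67). The n = 8 value depends on regional arm sizes that the SAP does not list: 67.3 with 16/10 and 15/11, which keeps 36/24 overall, and 69.6 with 16/10 twice. The n = 6 cell is about 2 points off.
- Six months, pure Poisson: Table 4 becomes 93 to 97% and Table 5 at least 99.7%. Every stated cell is missed by 8 to 33 points.
- Five Japanese subjects, mean, Method 2: stated 86%. Six-month Poisson gives 99.9%; with k of 0.5, 1 and 2 in both arms, about 94%, 87% and 75%.

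**The case against.** The basis is disclosed: both documents speak of monthly rates, and the SAP says which values were entered. The arithmetic reproduces, so this is a mismatch between power model and endpoint rather than a slip of calculation. Under the plan's own Poisson assumption the mismatch is conservative, and the 20 additional subjects have other reasons. All of that stands.

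The low power figures come only from dispersions that the documents do not contain, and k = 2 is extreme. A gamma distribution with mean 1.3 and k = 2 puts 38% of placebo subjects below the assumed CSL312 mean of 0.3125 per month. Eligibility requires at least 3 attacks in 3 months before Screening (or before prophylaxis was started) and at least 2 in the run-in. Entry rules do not fix on-study rates, so k = 2 is not excluded, but it belongs at the edge of the range. An even two-point placebo mixture with mean 1.3 and a homogeneous CSL312 arm gives power at 24/16 of 0.999, 0.99 and about 0.89 for assumed rate ratios of 3, 4 and 6. Moderate heterogeneity therefore does not by itself produce a shortfall.

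The one-month basis of Tables 4 and 5 is inferred from reproduction, and the exact match depends on unlisted regional splits. That too stands, but the six-month alternative misses every cell widely.

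None of this makes the 90%, or 40 as the lowest total, a property of the Day 1–182 endpoint.

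**Conclusion.** The concern holds. The stated 90% and the claim about the smallest N are correct for a single month's count at an exact 3:2 split, and incorrect for the primary endpoint. Under the plan's own model, power at 40 completers exceeds 99.9% and 10 to 15 completers would suffice. With between-subject variation, power at 40 runs from 0.99 (k = 0.5) through 0.82–0.88 (k = 1) to 0.35–0.59 (k = 2). At the planned 60, if all complete, the figures are above 0.99, 0.94–0.97 and 0.46–0.77.

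This does not show an underpowered trial. It shows that the power depends on a parameter the plan never states. The dispersion range is an assumption, and the one-month basis of Tables 4 and 5 is an inference. The sentence that 5 Japanese subjects already reach 80% (mean, Method 2) remains true under six-month Poisson and for k up to 1, but not at k = 2.

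**What to change.** Keep the sample size. Then:

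- Recompute power on 182-day counts with an explicit between-subject dispersion, informed by CSL312_2001 where it can be estimated. Protocol 1.2.3.2 says of that study: "A total of 32 patients with C1-INH HAE type 1 or type 2 were enrolled in the randomized double-blind treatment arms of TP1", spread over four groups. Any estimate will be imprecise, so show a range, for example 0.5 to 2, in both arms and in placebo only.
- Restate the power for 40 completers and for 60 randomized in protocol 10.1 and SAP 4.5.
- Delete the clause calling 40 the lowest total that reaches 90%.
- State the observation period and the regional arm sizes for Tables 4 and 5, and recompute both tables on the same basis as the power.

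The cost is re-running the power programs and editing two sections. Enrolment, test and alpha do not change.

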4.6 Planned Interim Analyses and Reviews

4.6.1 Interim Analyses Other Than Sample Size Re-estimation

No formal interim analyses are planned for this study.

4.6.2 Interim Sample Size Re-estimation

Interim sample size re-estimation is not applicable for this study.

4.6.3 Independent Data Monitoring Committee

An independent data monitoring committee (IDMC) will be established to monitor the safety and efficacy data generated during the study. The IDMC will consist of an independent statistician and clinical specialists in the fields of HAE management, who also have experience in clinical trials. The IDMC will review accumulating data from the ongoing study. Based on these reviews, the IDMC will advise on the further conduct of the study. No success or futility thresholds will be set for the IDMC reviews; CSL will not stop the study unless a major safety issue has been identified. The composition, activities, and responsibilities of the IDMC will be described separately in the IDMC charter. A separate IDMC SAP and IDMC TFL Shells will be created.

5 Changes from the Protocol Planned Analyses

Estimand definition has been updated to reflect the potential impact of the ongoing coronavirus disease 2019 (COVID-19) pandemic, see [Section 7.1](#) and [Section 10.1.1](#).

Comparison of the distribution of responses to therapy between CSL312 and placebo at the end of the Treatment Period will use the ~~cci~~ at Visit Day 182 only. If subject's Study Visit Day 182 ~~cci~~ value is missing the subject will not be included in the ~~cci~~, see [Section 10.4](#).

Also, hypothesis H02 and hypothesis H04 have been defined more clearly by modifying the wording, see [Section 4.2](#).

There are no further changes to the analyses planned compared to the CSP. Any changes conducted after finalization of the SAP will be noted in the Clinical Study Report.

6 Study Analysis Sets

